4.2.9 Sensitivity analysis

Considering the IPDs which could significantly affect the evaluation of efficacy endpoints may occur in the study, sensitivity analysis will be performed for PFS and OS excluding the patients with such IPDs.

These IPDs will be determined in the data review meeting before database lock and clearly documented.

5 INTERIM ANALYSES

There will be no formal interim analysis in this study.

As the safety of durvalumab + EP has not been previously established in ES-SCLC patients with PS2, a safety review committee (SRC) will be established to review the safety and tolerability data of the combination of durvalumab+EP in this subset of patients at an early stage of enrolment. SRC will include AZ local study team member such as study physician, PV physician, PM and local medical affairs Lead, and also global clinical lead, global patient safety physician and GMAL.

The SRC will meet after the first 20 patients with PS2 have either had the opportunity to complete the combination of durvalumab + chemotherapy (maximum of 6 cycles) or have discontinued treatment with durvalumab due to an AE or disease progression, whichever occurs first.

After review of the data in patients with PS2, and patients with PS0-1, the SRC will make a recommendation on whether the study should continue recruitment of patients with PS2 as planned, or hold recruitment of this patient population, or amend the study design. In the event that the SRC recommends a change to the study, this will be communicated to all sites.

The primary analysis of the study will be conducted 6 months after LSI, at which time secondary endpoints will also be assessed (maturity for PFS is anticipated to be approximately 60%).

Additionally, final analysis will be performed at the end of the study when all patients have completed follow-up for safety or sufficient maturity for the secondary efficacy objectives has been reached.

6 CHANGES OF ANALYSIS FROM PROTOCOL

No change of analysis from protocol is made.

8 APPENDIX

Appendix A Schedule of assessments

Visit	Screening	Treatment period			Safety follow-up visit	Survival follow-up phone calls/emails
		Baseline (Day1)	During Chemotherapy 1 cycle = 21 days	Post-Chemotherapy 1 cycle = 28 days		
Visit window	Day-28 to Day-1	0	±3 days	±3 days	±7 days	±14 days
Week	Weeks-4 to Week-1	Week 0	Week 3, 6, 9; Weeks 12, 15 at investigator discretion	3 weeks after last dose of chemotherapy (either Week 12, 15 or 18), then every 4 weeks until PD	90 days after last dose	Every 3 months
Written informed consent ^a	X					
Inclusion/exclusion criteria	X					
Demographics, including baseline characteristics	X					
Medical history, including cancer treatment history	X					

Visit	Screening	Treatment period			Safety follow-up visit	Survival follow-up phone calls/emails
		Baseline (Day1)	During Chemotherapy 1 cycle = 21 days	Post-Chemotherapy 1 cycle = 28 days		
Visit window	Day-28 to Day-1	0	±3 days	±3 days	±7 days	±14 days
Week	Weeks-4 to Week-1	Week 0	Week 3, 6, 9; Weeks 12, 15 at investigator discretion	3 weeks after last dose of chemotherapy (either Week 12, 15 or 18), then every 4 weeks until PD	90 days after last dose	Every 3 months
ECG recording ^b	X	As clinically indicated				
Physical examination, weight, and vital signs	X	X	X	X	X	
Concomitant medications	X	X	X	X	X	
Laboratory Assessments						
Clinical chemistry ^c	X	X ^d	X	X	X	
Hematology ^c	X	X ^d	X	X	X	
TSH, (reflex free T3 or free T4 ^f)	X	X ^e	X	X	X	
Hepatitis B, C, HIV virology	X					
Pregnancy test ^g	X	X	X	X	X	
Urinalysis	X	As clinically indicated				
Monitoring						
AE	X	X	X	X	X	
ECOG performance status	X	X	X	X	X	
IP Administration						
Durvalumab ^h		X	X	X		
Etoposide ⁱ		X	X ^k			
Carboplatin or cisplatin ^{ij}		X	X ^k			

Visit	Screening	Treatment period			Safety follow-up visit	Survival follow-up phone calls/emails
		Baseline (Day1)	During Chemotherapy 1 cycle = 21 days	Post-Chemotherapy 1 cycle = 28 days		
Visit window	Day-28 to Day-1	0	±3 days	±3 days	±7 days	±14 days
Week	Weeks-4 to Week-1	Week 0	Week 3, 6, 9; Weeks 12, 15 at investigator discretion	3 weeks after last dose of chemotherapy (either Week 12, 15 or 18), then every 4 weeks until PD	90 days after last dose	Every 3 months
Tumor assessment per Investigator - report (according to RECIST1.1) ^l	X	On study tumor assessments should occur at Week 6±2 weeks, at Week 12±2 weeks then every 8±2 weeks ^m until PD				
Subsequent anticancer therapy					X	X
Survival status					X	X

- a. Written informed consent and any locally required privacy act document authorization must be obtained prior to performing any protocol-specific procedures, including screening/baseline evaluations. If laboratory or imaging procedures were performed for alternate reasons prior to signing consent, these can be used for screening purposes with consent of the patient. However, all screening laboratory and imaging results must have been obtained within 28 days of first dose.
- b. Any clinically significant abnormalities detected require triplicate ECG results.
- c. Serum or plasma clinical chemistry (including LFT monitoring) and hematology may be performed more frequently if clinically indicated.
- d. If screening laboratory assessments are performed within 3 days prior to Day 1 (first infusion day), they do not need to be repeated at day 1.
- e. If TSH is measured within 14 days prior to Day 1 (first infusion day), it does not need to be repeated at Day 1.
- f. Free T3 or free T4 will only be measured if TSH is abnormal or if there is clinical suspicion of an AE related to the endocrine system.
- g. Pregnancy test will be performed in women of childbearing potential only. A urine or serum pregnancy test is acceptable. Women of childbearing potential are required to have a pregnancy test within 7 days prior to the first dose of study drug and then every 4 weeks. Pregnancy test may occur on Day 1, but results must be available and reviewed by the treating physician or Investigator prior to commencing an infusion.
- h. Results for liver function tests, electrolytes, full blood count, and creatininemust be available before commencing an infusion (samples taken within 3 days prior to infusion) and reviewed by the treating physician or Investigator prior to dosing.
- i. Durvalumab will be administered first, followed by the etoposide + cisplatin/carboplatin regimen.
- j. If cisplatin, infuse over 1 to 2 hours. If carboplatin, infuse over 0.5 to 1 hour.
- k. Chemotherapy regimen (etoposide plus either cisplatin or carboplatin) to be administered Q3W for 4 to 6 cycles, per investigator clinical decision.
- l. See protocol Section 6.1 and Appendix C for additional details relevant to image acquisition, RECIST 1.1 assessments, and evaluation of scans after RECIST 1.1-defined progression.
- m. Patients will have scans done Q6W for the first 12 weeks, and then Q8W thereafter or per institutional standard at investigator discretion.

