3.2.1 Derivation of RECIST visit responses

For all patients, the RECIST tumour response data will be used to determine each patient's visit response according to RECIST version 1.1. It will also be used to determine, if and when a patient's disease has progressed in accordance with RECIST and their best objective response to study treatment.

The baseline radiological tumour assessment is part of the screening procedure and should be performed no more than 28 days before the start of treatment, and ideally as close as possible to the start of study treatment. Tumour assessments will be at 6 weeks \pm 2 weeks after study treatment initiation, at 12 weeks \pm 2 weeks after study treatment initiation and then continue every 8 weeks \pm 2 weeks thereafter until disease progression. An additional follow-up scan will be performed if clinically feasible.

If an unscheduled assessment is performed, and the patient's disease has not progressed, every attempt should be made to perform the subsequent assessments at patients' scheduled visits. This schedule is to be followed to minimise any unintentional bias caused by some patients being assessed at a different frequency than other patients.

Additional scans can be completed per standard practice post-disease progression.

From the investigator's review of the imaging scans, the RECIST tumour response data will be used to determine each patient's visit response according to RECIST version 1.1. At each visit, patients will be programmatically assigned a RECIST 1.1 visit response of CR, PR, SD or PD, using the information from target lesions (TLs), non-target lesions (NTLs) and new lesions and depending on the status of their disease compared with baseline and previous assessments. If a patient has had a tumour assessment which cannot be evaluated, then the patient will be assigned a visit response of not evaluable (NE) (unless there is evidence of progression in which case the response will be assigned as PD).

RECIST outcomes (ie, PFS and ORR etc.) will be calculated programmatically from site investigator data from overall visit responses.

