3.2.3 PFS

PFS is defined as the time from first dose of study treatment until the date of objective disease progression or death (by any cause in the absence of progression) regardless of whether the patient withdraws from study therapy or receives another anti-cancer therapy prior to progression. Patients who have not progressed or died at the time of analysis will be censored at the time of the latest date of tumor assessment. However, if the patient progresses or dies after 2 or more missed visits, the patient will be censored at the time of the latest assessment. If the patient has no evaluable visits or does not have baseline data, they will be censored at the day of first dose unless they die within 2 visits of baseline (2 x 6 weeks for tumor assessments + 2 x 2 weeks for permitted visit window).

The PFS time will always be derived based on assessment dates not visit dates.

$PFS \text{ (months)} = (\text{Date of event or censoring} - \text{Date of first dose} + 1) / 30.4375$, results round to 1 decimal place. The cases of event and censoring are listed in Table 4 PFS calculation under various cases.

Given the scheduled visit assessment scheme (ie, q6w ± 2w for the first 12 weeks then q8w ± 2w thereafter) the definition of 2 missed visits will change. To evaluate the no. of missing tumor assessments between the first PD/death and the last non-missing tumor assessment before, following rules will be used.

Table 3 Criteria of at least 2 missing tumor assessments

Cases	Conditions when considered as at least 2 missing tumor assessments
There is 2 consecutive missed tumor assessments before first PD/death since first dose.	Time interval between first dose and first PD/death is >16 weeks (ie. 2 * 6 + 4 weeks, 112 days)
If the 2 consecutive missed tumor assessments occur over the period(Week 12) when the scheduled assessments changes from q6w to q8w	Time interval between the last tumor assessment and first PD/death is >18 weeks (ie. 6 + 8 + 4 weeks, 126 days)
If the 2 consecutive missed tumor assessments occur after Week 12 onwards	Time interval between the last tumor assessment and first PD/death is >20 weeks (ie. 2 * 8 + 4 weeks, 140 days)

Table 4 PFS calculation under various cases

Cases	Date used as the end of PFS	Event or Censoring
Patients with PD or death, and first PD or death are within 2 assessments after last tumor assessment before PD/death	Date of first PD or death	Event

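### Appendix A footnote m permits scan intervals other than 8 weeks, but Table 3 counts missed assessments by elapsed time that is valid only at 8 weeks, so PFS event status can be wrong for off-schedule patients

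*SAP*

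**What the plan says.** Section 3.2.1 sets scans at Weeks 6 and 12, "and then continue every 8 weeks" (±2 weeks) until progression, and gives the reason: "This schedule is to be followed to minimise any unintentional bias caused by some patients being assessed at a different frequency than other patients". Section 3.2.3 and the tumour-assessment row of the Appendix A grid repeat the 8±2-week interval.

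Footnote m, attached to that row, allows Q6W scans for 12 weeks "and then Q8W thereafter or per institutional standard at investigator discretion". It sets no lower or upper limit on the alternative interval.

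Section 3.2.3 says that "if the patient progresses or dies after 2 or more missed visits, the patient will be censored at the time of the latest assessment". Table 4 repeats the principle. Table 3 turns it into elapsed time. From Week 12 onwards the condition is "Time interval between the last tumor assessment and first PD/death is >20 weeks (ie. 2 * 8 + 4 weeks, 140 days"). Across the Week 12 change of schedule it is "Time interval between the last tumor assessment and first PD/death is >18 weeks (ie. 6 + 8 + 4 weeks, 126 days"). Table 3 has no row for any other interval.

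**The concern.** Footnote m permits the unequal scan frequency that 3.2.1 sets out to prevent, and this reaches the derivation of PFS. Table 3 does not look at which planned scans were absent. It compares a gap in days with a limit built from 6- and 8-week intervals. For a patient properly scanned at another interval, the gap no longer tells one missed scan from two. Table 3 can then give one event status, and the text of 3.2.3 with Table 4 the opposite one. The SAP does not say which governs.

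PFS is affected directly. APF12 is affected because it is the Kaplan-Meier estimate of PFS at 12 months (3.2.4), and DoR because its end must match the PFS date (3.2.6). The only sensitivity analysis in 4.2.9 excludes patients with important protocol deviations. Scanning under footnote m is permitted, so it would not ordinarily be a deviation, and that analysis does not address the problem.

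**Working it through.** **Inputs from the SAP.** Scan window ±2 weeks (3.2.1); Table 3 limits of 16, 18 and 20 weeks; censoring after two or more missed assessments (3.2.3, Table 4). **Assumed.** The alternative interval, which footnote m leaves open; 6 to 12 weeks is tabulated below.

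**The plan's own limits reproduce.** 2×6+4 = 16 weeks (112 days); 6+8+4 = 18 weeks (126 days); 2×8+4 = 20 weeks (140 days).

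**Formula.** With interval x weeks and k missed scans, the nominal gap from the last scan to the scan showing progression is (k+1)x. Each end can move by 2 weeks, so the range is (k+1)x − 4 to (k+1)x + 4.

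**Against the 20-week limit (after Week 12):**

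| Interval x | One missed: nominal (range) | Two missed: nominal (range) | Result |
|---|---|---|---|
| 6 weeks | 12 (8–16) | 18 (14–22) | event usually kept after two missed |
| 8 weeks | 16 (12–20) | 24 (20–28) | works as intended |
| 9 weeks | 18 (14–22) | 27 (23–31) | one missed can be censored |
| 10 weeks | 20 (16–24) | 30 (26–34) | one missed can be censored |
| 12 weeks | 24 (20–28) | 36 (32–40) | one missed censored on nominal dates |

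One missed scan can exceed the limit when 2x + 4 > 20, that is x > 8 weeks. It does so on nominal dates when 2x > 20, that is x > 10 weeks.

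**Against the 18-week limit** (last scan Week 6, Week 12 missed, next scan at Week 12 + x). The nominal gap is 6 + x. At x = 8 it is 14 (10–18), never above 18. At x = 12 it is 18 (14–22), so one missed scan can be censored.

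**Deaths.** At x = 12, a death 21 weeks after the last scan follows one missed scan on nominal dates (the one due at 12 weeks; the next is due at 24). Table 3 still censors it, because 21 > 20.

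**Illustration of size.** Simulation with 30,000 patients per scenario. Assumptions: exponential time to progression with median 5 to 7 months; 5% to 10% of scans missed at random; ±1 week jitter in scan dates; Table 3 limits applied. The APF12 change is the Kaplan-Meier rate under Table 3 minus the rate with every event counted.

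| Scenario | Censored with fewer than two missed | APF12 change |
|---|---|---|
| All patients on 8-week scans | 0.0% | none from misclassification |
| All patients on 12-week scans | about 6% to 12% | about +0.7 to +2.5 points |
| 20% on 12-week scans (median 6 months, 10% missed) | about 2% | about +0.7 points |

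In the last row, about 0.3 to 0.4 points come from censoring that the rule intends (two or more scans really missed). That leaves about 0.7 − 0.4 = 0.3 to 0.7 − 0.3 = 0.4 points from misclassification.

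**The case against.** The strongest defence is that the stakes are small and partly visible. PFS, APF12 and DoR are secondary and descriptive, and nothing is tested on them. Section 4.2.5.1 summarises the numbers of events and censorings by case. Read with Table 4, that would show how many patients were censored for missed assessments. No 12-week interval and no share of off-schedule patients appears in the SAP, so any figure rests on assumption. All of this stands, and it limits the size of the point. It does not remove it: the count would not separate patients who missed one scan from those who missed two, and it would not correct their event status.

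A reader might also infer stronger things that the document does not support:

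- *That progression would be censored with no scan missed.* This needs x + 4 > 20, an interval above 16 weeks with both windows at their extremes, or above 20 weeks on nominal dates. The SAP names no such interval, and at 12 weeks the gap without a missed scan is at most 16 weeks.
- *That the error always flatters the treatment.* Intervals below 8 weeks err the other way, by keeping events after two missed scans.
- *That Table 3 distorts median PFS.* In the simulations, medians with Table 3 applied or ignored differ by at most 0.03 months. Differences in the median between scan intervals come from the spacing of scan dates and can go in either direction.

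**Conclusion.** The point holds as a conflict between footnote m and the schedule in 3.2.1, 3.2.3 and the Appendix A grid, with a consequence for the PFS derivation. For a patient scanned at a permitted interval longer than 8 weeks, Table 3 can censor a progression or death after a single missed scan, contrary to 3.2.3 and Table 4. For a shorter interval it can keep an event after two missed scans.

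For patients actually on the 8-week schedule, the rule works and no one is wrongly censored. The trial-level effect cannot be computed, because the share of patients off that schedule and their intervals are not given; the illustrative figures depend on the assumed interval, missed-scan rate and median. OS and the primary safety endpoints are unaffected. The matter should be corrected because the plan, followed as written, gives the wrong event status for patients it allows.

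**What to change.** 1. Reconcile footnote m with 3.2.1, 3.2.3, Table 3 and the Appendix A grid, so that they agree on whether intervals other than 8 weeks are allowed.
2. If they are, state in 3.2.3 that for any patient not on 8-week scans, missed assessments are counted against that patient's own planned scan dates (two consecutive planned scans absent), in place of the fixed 126 and 140 days.
3. Add to 4.2.9 a sensitivity analysis of PFS and APF12 that counts every progression or death at its actual date, regardless of missed scans.

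The cost is SAP wording, one extra analysis and slightly more programming. Planned scan dates must be derived for off-schedule patients, which requires the intended interval to be known for each of them.

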Appendix B TFL mock shells

Please refer to the independent appendix document containing all TFL mock shells.

Appendix C SDTM and ADaM specifications

Please refer to the independent appendix documents for the specifications.
